3.3.2 Exclusion Criteria

1. Target Disease Exceptions

- a) Cohort 1 and 2, Arms A and B: Active CNS metastases (including evidence of cerebral edema by CT scan or MRI, progression from prior imaging study, any requirement for steroids or clinical symptoms of/from CNS metastases) within 28 days of study enrollment.
- b) Cohort 1 and 2, Arms A and B: Subjects with known metastases must have a repeat imaging brain scan within 28 days of randomization/registration. If progression in prior lesion(s) or new lesion(s) is/are detected on repeat brain scan, patients are excluded from study.
- c) Arms D and E: History of carcinomatous meningitis (lumbar puncture is not required).
- d) Arms D and E: Radiation within 14 days prior to initiation of study therapy, and the radiation field cannot have included the index brain lesion.

2) Medical History and Concurrent Diseases

- a) Participation in a blinded trial or study which has not yet completed final database lock and has not been unblinded for primary endpoint analysis
- b) Subjects with other concomitant malignancies, except basal cell or squamous cell skin cancers, superficial bladder cancer, or carcinoma in situ of the cervix or breast, are excluded unless a complete remission was achieved at least 2 years prior to study entry and no additional therapy is required or anticipated to be required during the study period
- c) Subjects with active autoimmune disease, a history of known or suspected autoimmune disease or a history of a syndrome requiring systemic corticosteroids (> 10 mg daily prednisone equivalent), cytotoxic therapy or immunosuppressive medications with the exception of:
 - i. Isolated vitiligo
 - ii. Resolved childhood atopy
 - iii. The history of positive ANA titer without associated symptoms or history of symptoms of an autoimmune disorder
 - iv. Controlled thyroid disorders
- d) Positive tests for human immunodeficiency virus (HIV 1/2) antibody (may obtain additional testing or substitute testing per institutional guidelines to rule out infection), or known acquired immunodeficiency syndrome (AIDS)
- e) History of any chronic hepatitis including alcoholic, non-alcoholic steatohepatitis (NASH), drug related, autoimmune, chronic viral
 - i. Positive tests for hepatitis B virus surface antigen (HBsAg) or
 - ii. hepatitis C antibody (may obtain additional testing or substitute testing per institutional guidelines to rule out infections)
- f) Evidence of active infection ≤ 7 days prior to initiation of study drug therapy.
- g) Prior organ allograft or allogenic bone marrow transplantation.

- h) Uncontrolled or significant cardiovascular disease including, but not limited to, any of the following:
 - i. Myocardial infarction within the past 6 months
 - ii. Uncontrolled angina within the past 3 months
 - iii. History (family or personal) of congenital long QT syndrome
 - iv. Any history of clinically significant arrhythmias (such as ventricular tachycardia, ventricular fibrillation or Torsades de pointes)
 - v. Controlled atrial fibrillation by itself is not an exclusion criterion
 - vi. History of other clinically significant heart disease (i.e. cardiomyopathy, NYHA functional classification III-IV)
 - vii. Requirement for daily supplemental oxygen therapy
- i) Known or underlying medical condition (e.g., a condition associated with diarrhea, diverticulitis, neuropathy or atopy) that, in the Investigator's opinion, would make the administration of study drug hazardous to the subjects or obscure the interpretation of toxicity determination or adverse events
- j) Subjects with evidence of bleeding disorder deemed unsafe by the Investigator to undergo biopsies
- k) Subjects who are unable to undergo venipuncture and/or to tolerate venous access.
- l) Subjects who have undergone any major surgery within 4 weeks of study drug administration
- m) Subjects with psychiatric illness or social situations that would preclude study compliance or the ability to tolerate study procedures and or study therapy.
- n) Subjects with the presence of underlying medical condition that in the opinion of the Investigator or Sponsor could adversely affect the ability of the subject to comply with or tolerate study procedures and/or study therapy

3) Allergies and Adverse Drug Reaction

- a) History of allergy to components of the study drug or known allergy to antibody therapies
- b) Subjects with a known history of the following anti-CTLA4 therapy related adverse reactions based on the CTCAE v4.0 criteria:
 - i. Any \geq grade 3 anti-CTLA4 mAb related dose-limiting adverse reaction
 - ii. Any anti-CTLA4 mAb related event requiring permanent discontinuation of therapy regardless of grade
 - iii. Any adverse reaction that did not resolve with steroids alone (i.e. required infliximab, mycophenolate or cyclophosphamide)
 - iv. Any Grade \geq 3 non-laboratory anti-CTLA4 therapy related adverse reaction except for:
 - (a) Endocrinopathies where clinical symptoms were controlled with appropriate hormone replacement therapy
 - (b) Nausea
 - (c) Fatigue

- v. Any Grade ≥ 3 laboratory abnormalities except for:
 - (a) Any Grade ≥ 3 lymphopenia
 - (b) Any transient Grade ≥ 3 electrolyte abnormalities that occurred while on anti-CTLA4 therapy that were not associated with clinical symptoms and responded with 72 hours
 - (c) Any AST, ALT or T. bilirubin such that:
 - (i) AST or ALT $> 10 \times$ ULN
 - (ii) Total bilirubin $> 5 \times$ ULN
- vi. Any \geq Grade 2 eye pain or reduction of visual acuity that did not respond to topical therapy and did not improve to \leq Grade 1 severity within 2 weeks of starting topical therapy or required systemic treatment.
- vii. History of Grade ≥ 3 neurologic toxicity

4) Sex and Reproductive Status

- a) WOCBP who are **unwilling or unable** to use an acceptable method to minimize the risk of pregnancy for the entire study period and for at least 23 weeks after the last dose of investigational product.
- b) Women who are pregnant or breastfeeding.
- c) Women with a positive pregnancy test on enrollment or prior to investigational product administration.
- d) Sexually active fertile men not using effective birth control when their partners are WOCBP for at least 31 weeks after the last dose of investigational product.

5) Prohibited Prior Treatments and/or Therapies

- a) Subjects who have received prior treatment with T cell coregulatory protein targeted therapies including but not limited to, anti-PD-1, anti-PD-L1, anti-PD-L2, anti-CD137, anti-OX-40, anti-CD40 in the adjuvant or metastatic setting are ineligible to participate in the study. Prior anti-CTLA4 monoclonal antibody therapy is permitted for cohort 2.
 - i. Prior cytokine therapy **is** allowed (e.g. interferon or interleukin-2).
- b) Exposure to any other investigational drug within 4 weeks of study drug administration
- c) Any anti-cancer therapy (e.g., chemotherapy, biologics, vaccines, radiotherapy, or hormonal treatment) within 5 half lives or within a maximum of 4 weeks of study drug administration (if 5 half-lives is longer than 4 weeks)
- d) Use of non-oncology vaccines (live, attenuated, or inactivated) against infectious diseases (for example, MMR, polio, Pneumovax®, Zostavax®, Flumist®) within 4 weeks (28 days) of initiation of study therapy
 - i. Use of the seasonal killed influenza vaccine is allowed without restriction.
- e) Use of growth factors, including, but not limited to, granulocyte-colony stimulating factor (G-CSF), granulocyte macrophage-colony stimulating factor (GM-CSF) or erythropoietin within 4 weeks of study drug therapy

- f) Use of pRBC or platelet transfusion 4 weeks prior to study drug therapy
- g) Systemic corticosteroids must be ≤ 10 mg daily prednisone equivalents 4 weeks before the first dose of study therapy. Subjects requiring long term immunosuppression are not eligible.
- h) Use of anti-RANKL therapy (i.e. denosumab as Xgeva® or Prolia®) within 140 days (5 half-lives) prior to study drug administration
- i) Use of oral or intravenous bisphosphonate therapy (e.g. zoledronic acid, alendronate or risedronate) less than 5 half-lives prior to study drug administration
- j) Use of herbal over-the-counter (OTC) supplements is not permitted. Concerns regarding specific OTC therapies may be discussed with the medical monitor.

6) Other Exclusion Criteria

- a) Prisoners or subjects who are involuntarily incarcerated
- b) Subjects who are compulsorily detained for treatment of either a psychiatric or physical (e.g. infectious disease) illness

Eligibility criteria for this study have been carefully considered to ensure the safety of the study subjects and to ensure that the results of the study can be used. It is imperative that subjects fully meet all eligibility criteria.

No exceptions to these criteria will be granted by the Sponsor.

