3.3.1 Inclusion Criteria

1) Informed Consent:

- a) Signed, written Informed Consent must be obtained prior to the performance of any study related procedures that are not considered part of standard of care

2) Target Population:

- a) Subjects with advanced melanoma (unresectable or metastatic) who have received and either progressed or discontinued on no more than 3 prior treatment regimens or have refused standard therapy for treatment of metastatic melanoma.
 - i. Subjects may have been treated or offered treatments for melanoma (e.g., chemotherapy, biological therapy, targeted therapy, vaccine therapy or cytokine therapy).
 - ii. Subjects who have never received any treatment for metastatic disease, ie. newly diagnosed subjects, may be allowed on study if they have been offered and have refused standard therapy or are deemed to be inappropriate candidates for standard therapy by the investigator.
 - iii. Subjects enrolled to Cohort 1 and Arms A, B, D and E (see [Figure 3.1](#)) must never have received anti-CTLA4 therapy (anti-CTLA4 naive).
 - iv. Subjects enrolled to cohort 2 (see [Figure 3.1](#)) must have had anti-CTLA4 monoclonal antibody (mAb) based therapy as 1 of the prior regimens (anti-CTLA4 progressors). If anti-CTLA4 mAb therapy was the last treatment regimen prior to study entry, the last dose of anti-CLTA4 mAb must have been administered at least 6 weeks prior to initiation of study therapy. Relapse during or within 6 month of last dose of anti-CTLA4 mAb adjuvant treatment for completely resected melanoma alone will also fulfill this criterion.
 - v. Subjects enrolled to Arms D and E
 - (1) Must have at least one measurable index brain metastases > 0.5 cm and not larger than 3 cm that has not been previously irradiated

- (2) Index brain lesions must not have sequela of prior therapy that would confound attribution of tumor response including edema or hemorrhage
 - (3) Must not have neurologic symptoms secondary to metastatic lesions
 - (4) Must not have received systemic corticosteroids within 14 days prior to initiation of study therapy.
- b) Subjects must have histologic confirmation of advanced melanoma. Confirmation of diagnosis must be obtained from the pre-treatment biopsy if it is not available from a prior diagnostic procedure.

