 - v. Total bilirubin $\leq 1.5\text{x}$ the institutional upper limit of normal (IULN)
 - vi. Subjects with Gilbert's syndrome are eligible if their total bilirubin is less than 3.0 mg/dl
 - vii. ALT (alanine aminotransferase) and AST (aspartate aminotransferase) $\leq 3\text{x}$ IULN
 - viii. Estimated GFR (eGFR) calculated via MDRD or Cockcroft-Gault equations $\geq 40 \text{ mL/min}$
- i) Known BRAF V600 mutation status (Parts 2, 3 and 4). Subjects with either V600 wild-type or V600 mutation-positive status, are eligible.

3) Age and Reproductive Status:

- a) Males and females ≥ 16 years of age.
- b) Women of childbearing potential:
 - i. Women of childbearing potential (WOCBP) must use method(s) of contraception based on the tables in [Appendix 3](#). A highly effective method(s) of contraception (failure rate of less than 1% per year) is required. The individual methods of contraception should be determined in consultation with the investigator. WOCBP must follow instructions for birth control when the half life of the investigational drug is greater than 24 hours, contraception should be continued for a period of 30 days plus the time required for the investigational drug to undergo five half lives (total of 23 weeks after the last dose of investigational product).
 - ii. Women must have a negative serum or urine pregnancy test (minimum sensitivity 25 IU/L or equivalent units of HCG) within 24 hours prior to the start of investigational product.
 - iii. Women must not be breastfeeding.
- c) Men who are sexually active with WOCBP must use any contraceptive method with a failure rate of less than 1% per year. Men that are sexually active with WOCBP must follow instructions for birth control when the half life of the investigational drug is greater than 24 hours, contraception should be continued for a period of 90 days plus the time required for the investigational drug to undergo five half lives (total of 31 weeks after the last dose of investigational product).
- d) Women who are not of childbearing potential (ie, who are postmenopausal or surgically sterile; see [Section 3.3.3](#) for the definition of WOCBP) and azoospermic men do not require contraception.

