4.3.5 Study Drug Discontinuation Criteria due to Adverse Event(s)

Study drug administration must be discontinued if at least one of the following drug related adverse event(s) occurs:

- Any \geq Grade 2 eye pain or reduction of visual acuity that does not respond to topical therapy and does not improve to Grade 1 severity within 2 weeks of starting therapy OR requires systemic treatment;
- Any \geq Grade 3 non laboratory drug-related adverse event with the exception of fatigue, and endocrine drug related AEs which are stable with hormone replacement therapy
- Any \geq Grade 3 bronchospasm, hypersensitivity reaction, or infusion reaction;
- Any patient that experiences any grade allergic/infusion reaction while receiving study drug at a slower infusion rate and/or with premedication due to a prior allergic/infusion reaction
- Any drug-related Grade 4 laboratory abnormalities, (except lymphopenia, asymptomatic lipase or amylase increases, or any electrolyte abnormality without any clinical sequelae that is either spontaneously reversible or resolves with clinical management to grade 2 or less within 72 hours)

- Hepatotoxicity as evidenced by any of the following:
 - AST or ALT > 5 - 10x ULN for >2 weeks
 - AST or ALT > 10 ULN
 - Total bilirubin > 5 x ULN
 - Concurrent AST or ALT > 3 x ULN and total bilirubin > 2 ULN (potential Hy's Law case)
- Any adverse event, laboratory abnormality or intercurrent illness, which in the judgment of the Investigator, presents a substantial clinical risk to the subject
- All adverse events that meet discontinuation criteria, as well as any Grade 3 or 4 infusion reactions must be reported to BMS, within 24 hours using the rapid notification procedures described in [Section 6.1.1](#).

Subjects who experience AEs that require discontinuation while receiving both nivolumab and ipilimumab may be allowed to continue therapy with nivolumab only if deemed in their best interest by both the PI and the BMS medical monitor. This will be decided on a case by case basis and will require convincing evidence that the benefit outweighs the risk.

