Patients on IV steroids may be switched to an equivalent dose of oral corticosteroids (e.g. prednisone) at start of tapering or earlier, once sustained clinical improvement is observed. Lower bioavailability of oral corticosteroids should be taken into account when switching to the equivalent dose of oral corticosteroids.

Hepatic Adverse Event Management Algorithm

Rule out non-inflammatory causes. If non-inflammatory cause, treat accordingly and continue I-O therapy. Consider imaging for obstruction.

[figure not shown]
Patients on IV steroids may be switched to an equivalent dose of oral corticosteroids (e.g. prednisone) at start of tapering or earlier, once sustained clinical improvement is observed. Lower bioavailability of oral corticosteroids should be taken into account when switching to the equivalent dose of oral corticosteroids.

*I-O therapy may be delayed rather than discontinued if AST/ALT ≤ 8 x ULN or T.bili ≤ 5 x ULN.

**The recommended starting dose for grade 4 hepatitis is 2 mg/kg/day methylprednisolone IV.

Endocrinopathy Management Algorithm

[figure not shown]
Rule out non-inflammatory causes. If non-inflammatory cause, treat accordingly and continue I-O therapy. Consider visual field testing, endocrinology consultation, and imaging.

Patients on IV steroids may be switched to an equivalent dose of oral corticosteroids (e.g. prednisone) at start of tapering or earlier, once sustained clinical improvement is observed. Lower bioavailability of oral corticosteroids should be taken into account when switching to the equivalent dose of oral corticosteroids.

Skin Adverse Event Management Algorithm

Rule out non-inflammatory causes. If non-inflammatory cause, treat accordingly and continue I-O therapy.

[figure not shown]
Patients on IV steroids may be switched to an equivalent dose of oral corticosteroids (e.g. prednisone) at start of tapering or earlier, once sustained clinical improvement is observed. Lower bioavailability of oral corticosteroids should be taken into account when switching to the equivalent dose of oral corticosteroids.

*Refer to NCI CTCAE v4 for term-specific grading criteria.

^If SJS/TEN is suspected, withhold I-O therapy and refer patient for specialized care for assessment and treatment. If SJS or TEN is diagnosed, permanently discontinue I-O therapy.

Neurological Adverse Event Management Algorithm

[figure not shown]

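### Exclusion 3(b)(v)(c) is inverted as written: it exempts the highest prior anti-CTLA4-related liver values, leaving a narrow safety gap in Cohort 2

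*Protocol*

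**What the plan says.** Exclusion 3(b) in Protocol Section 3.3.2 lists anti-CTLA4-related reactions that make a subject ineligible. Clause (v) covers Grade ≥ 3 "laboratory abnormalities except for" three items:

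- (a) lymphopenia;
- (b) transient electrolyte changes without symptoms that responded within 72 hours;
- (c) "Any AST, ALT or T. bilirubin such that" (i) AST or ALT is above 10 x ULN, (ii) total bilirubin is above 5 x ULN.

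Two other places deal with liver values of this size. Section 4.3.5 requires study drug to stop for "AST or ALT > 10 ULN", for total bilirubin above 5 x ULN, and for "AST or ALT > 5 - 10x ULN for >2 weeks". A footnote to the hepatic algorithm in Appendix 4 states that "I-O therapy may be delayed rather than discontinued if AST/ALT ≤ 8 x ULN or T.bili ≤ 5 x ULN".

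Section 3.3 and the end of Section 3.3.2 both say that no exceptions to the eligibility criteria will be granted.

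**The concern.** Items (a) and (b) are findings the sponsor is content to tolerate. Item (c) stands at the same level of the same list, yet it describes severe liver injury. An investigator who follows the text would admit the subject with the higher prior value and refuse the one with the lower.

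The stake is subject safety in Cohort 2, together with an accurate account of who was enrolled. A subject admitted under the literal reading is not a protocol deviation, so nothing in the planned deviation reporting would bring that subject to light.

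**Working it through.** No figure in the plan is involved and no calculation is needed. The check sets the texts side by side, then asks what the other criteria leave uncovered.

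**1. Direction of the rule**

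| Place | Value | Consequence |
|---|---|---|
| 3.3.2, 3(b)(v)(c), literal | Prior AST/ALT > 10 x ULN, bilirubin > 5 x ULN | Exempt from exclusion |
| 3.3.2, 3(b)(v), literal | Prior Grade ≥ 3 value at or below those limits | Excluded |
| 4.3.5 | On-study AST/ALT > 10 x ULN, or bilirubin > 5 x ULN | Must stop drug |
| Appendix 4 footnote | AST/ALT ≤ 8 x ULN or bilirubin ≤ 5 x ULN | Delay allowed instead of stopping |

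Section 4.3.5 carries the same two limits with the same sign, but there they mark what is not tolerated. Placed under an exception, the sign has to turn round. The text does not say whether (i) and (ii) are joined by *and* or *or*; the inversion is there either way. No other text restates the criterion correctly.

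**2. Who can be affected**

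Cohort 1 (about 40), Part 2 (about 20), Part 3 (about 30) and Part 4 (about 20) must all be anti-CTLA4 naive under inclusion 2(a)(iii): 40 + 20 + 30 + 20 = 110. Exclusion 3(b) cannot bite on them. That leaves Cohort 2: 150 − 110 = about 40.

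**3. What other criteria still catch**

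- 3(b)(i): Grade ≥ 3 dose-limiting reactions.
- 3(b)(ii): events that ended anti-CTLA4 therapy permanently.
- 3(b)(iii): reactions that steroids alone did not resolve.
- 2(c): autoimmune disease, or a syndrome that needed more than 10 mg/day prednisone equivalent.
- 2(e): chronic hepatitis, including drug-related.
- 2(i) and 2(n): conditions judged unsafe by the investigator or sponsor.
- Inclusion 2(h): ALT and AST ≤ 3 x IULN and bilirubin ≤ 1.5 x IULN at entry.

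**4. What is left**

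The remaining case is a severe rise that limited no dose, did not stop therapy, recovered to the entry limits and fell outside 2(c). One example is a rise after the last planned anti-CTLA4 dose that settled without systemic steroids. Where anti-CTLA4 was the last regimen, inclusion 2(a)(iv) requires at least 6 weeks since the last dose, so recovery before entry is possible. Exclusions 2(i) and 2(n) rest on opinion and do not replace an objective limit.

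**5. Whether the analysis would reveal it**

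The programmed entry deviations in SAP Section 7.2.3 do not include exclusion 3(b). The same section sends non-programmable eligibility deviations to separate listings, but a subject counted as eligible under the literal text would appear in neither.

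**The case against.** The strongest case is that the wording is wrong but little follows from it.

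- **Timing.** Section 4.3 puts subjects enrolled after Amendment 04 into Arms A, B, D or E, all anti-CTLA4 naive. Correcting the line is therefore unlikely to change any future entry decision. This stands. The criterion is not wholly spent, however: Section 4.3.8 makes treatment beyond progression depend on still meeting the other eligibility criteria.
- **The protocol text in force for Cohort 2 is unseen.** Cohort 2 enrolled before Amendment 04, under protocol text that is not provided. This also stands, and it limits what can be said about exposure. It does not affect the reading of the current text.
- **The gap is close to hypothetical.** A subject must pass every criterion in step 3, and Appendix 4 calls corticosteroids a primary therapy for drug-related events of this kind. It is fair to call the gap narrow, but it is not closed.
- **On-study protection.** Cohort 2 receives nivolumab alone, with liver panels at each dosing visit, a hold above 3 x ULN for ALT or AST, and the Section 4.3.5 stopping rules. Section 4.3.5 also lets some subjects continue nivolumab alone, case by case, after toxicity on the combination. These reduce the risk after entry. They do not justify an entry rule that points backwards.
- **Appendix 4 is weak support.** The footnote belongs to a figure that is not shown. Agreed; Section 4.3.5 is enough without it.

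**Conclusion.** The point holds. The criterion is inverted as written, and it should be corrected because it is an operative safety rule.

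Its reach is small: at most about 40 Cohort 2 subjects and none elsewhere. The number with prior AST/ALT above 10 x ULN or bilirubin above 5 x ULN cannot be derived from the documents and may be zero. The retrospective part assumes that the versions under which Cohort 2 enrolled carried the same wording, which the documents do not show. There is no effect on the primary endpoint or the sample size, and no bias in the hepatic adverse event rate has been demonstrated.

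**What to change.** - Reverse item (c) so that the exception covers only Grade ≥ 3 AST or ALT at or below 10 x ULN and total bilirubin at or below 5 x ULN. State that a value above either limit excludes.
- Have the clinical team confirm the AST/ALT limit, since Appendix 4 uses 8 x ULN and Section 4.3.5 also stops drug for values of 5 to 10 x ULN that persist beyond two weeks.
- Check the wording in force when Cohort 2 enrolled. Then review those subjects' anti-CTLA4 liver history, using the screening medical history, which under Table 5.1A records toxicities of previous treatments.
- List any subject above the limits, and state in the clinical study report which reading was applied.

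The cost is one line of eligibility text, a single review of about 40 histories already collected, and one sentence in the report.
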